3.0 Inclusion/Exclusion Criteria

Inclusion criteria

- Men and women with a stable symptomatic claudication for ≥ 6 months
- Ankle brachial index < 0.9

Exclusion criteria

- Uncontrolled Diabetes (HbA1C > 8.5 measured within 3 months prior to date of consent)
- Heart Failure
- COPD
- Critical limb ischemia (ischemic rest pain or ischemia-related non healing wounds or tissue loss)
- Prior amputation
- Exercise-limiting comorbidity (i.e., angina, chronic lung disease, or arthritis)
- Recent (<3 months) infrainguinal revascularization (surgery or endovascular revascularization) or revascularization planned during study period.
- Plans to change medical therapy during the duration of the study
- Active cancer
- Chronic kidney disease (eGFR <30 by MDRD or Mayo or Cockcroft-Gault formula).
- HIV positive, active HBV or HCV disease.
- Presence of any clinical condition that in the opinion of the principal investigator makes the patient not suitable to participate in the trial.
- Peripheral neuropathy, numbness, or paresthesia in the legs.
- Morbid obesity BMI > 36 or unable to fit into water-circulating pants.
- Open wounds or ulcers on the extremity.

As this study involves MR imaging, patients that have contraindications to MRI will be included in the study but will not be allowed to participate in the MRI procedure. Information about biomedical devices that may pose a risk to patients undergoing MRI is available on the Internet at www.MRIsafety.com. These exclusions include:

- Cardiac pacemaker
- Implanted cardiac defibrillator
- Aneurysm clips
- Carotid artery vascular clamp
- Neurostimulator
- Insulin or infusion pump
- Implanted drug infusion device
- Bone growth/fusion stimulator
- Cochlear, otologic, or ear implant
- History of claustrophobia or who are unable to lie flat or who do not fit inside the bore of the scanner

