5.0 Study Procedures

After enrollment, subjects will be asked to complete two experimental sessions for baseline testing. The procedures involved in each visit, location and estimated duration are listed on Table 1. On **visit 1**, demographic and anthropometric characteristics from participants will be initially recorded. Subjects will then be asked about comorbid conditions, claudication history, and current medications and will fill out two questionnaires to assess generic (36-item Short-Form Health Survey) and disease-specific (Walking Impairment Questionnaire) quality of life. Next, subjects will be escorted to the examination room and will be asked to rest quietly for 15 min in the supine position. During this time, four NIRS (near infrared spectroscopy) sensors (Figure 2) will be attached to subjects’ two fingertips and two toes (left and right). These sensors are the same as the pulse oximeters used regularly in the hospital. We will monitor the blood flow during these 15 minutes while subjects are resting. After this rest period, systolic blood pressure will be measured in the arms (brachial artery) and ankles (posterior tibial and dorsalis pedis arteries) for the determination of the ankle brachial index. Subjects will then be familiarized with the 6-min walking test. A near-infrared spectroscopy (NIRS) system will be placed on the calf of the most symptomatic leg for monitoring leg oxygenation during the test. This exercise test consists of walking back and forth along a 100-ft corridor for 6 min. This session will be performed at the CTSI’s Clinical Research Center on the 5th floor of Goodman Hall and is expected to last approximately 2 hours.

Figure 2: Multichannel NIRS used to monitor the blood flow at two toes and two fingertips.

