Visit 2 will involve the assessment of the primary study outcomes, including vascular function and exercise tolerance. This session is expected to last approximately 4 hrs. Subjects will be asked to fast overnight prior to attending this session but will be permitted to take their usual morning medication regimen. The first exam will be the assessment of leg blood flow responses to circulatory occlusion (reactive hyperemia) using magnetic resonance imaging. This test will be performed at the Imaging Research Facilities in the basement of Goodman Hall. Next, subjects will be escorted to the CTSI's Clinical Research Center on the 5th floor. Subjects will initially be asked to lay supine and a nurse will place a catheter in one antecubital vein in the arm for venous blood sampling. After 10 min of rest, systolic blood pressures in the arms and in the ankles will be measured for the determination of the ankle-brachial index. Once the measurements are complete, a blood sample (20 ml) will be taken and the catheter will be removed. Next, subjects will be instrumented with laser Doppler probes placed inside local heaters for the assessment of cutaneous vascular reactivity. Two probes will be placed on the front portion of the most symptomatic leg and secured in place with tape. The sites where the probes are placed will be marked with a pen to allow for consistent placement in the second and third outcome measurement visits. The protocol consists of heating a site in the skin and measuring the changes in cutaneous red blood cell flux in response to the thermal challenge. Blood pressure and heart rate will be monitored during the test. This procedure will last approximately one hour. Next, the patients will perform the 6-min walking test. A near-infrared spectroscopy system, which measures skeletal muscle oxygenation, will be placed on the calf of the most symptomatic leg, secured in place with tape and covered with aluminum foil and a black Velcro strap. Similar to the laser Doppler probes, pen marks will be used identify the location of the probe. Subjects will be asked to walk back and forth along a 100-ft corridor for 6 min and report when the pain first appears. After the test is completed, subjects will be asked to grade the severity of the pain in the most symptomatic leg using the Borg-scale.

Visit #	Procedures	Location	Duration

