1	
 1) Medical History and Physical Examination 2) Quality of life assessment 3) Measurement of ankle-brachial index 4) Familiarization with the 6-min walking test 	CTSI's Clinical Research Center at Goodman Hall	2 hrs
2	
 1) Leg MRI (reactive hyperemia) 2) Catheter placement and venous blood draw 3) Measurement of ankle-brachial index 4) Assessment of cutaneous vascular function 5) 6-min walking test 	Imaging Research Facilities and CTSI's Clinical Research Center at Goodman Hall	4 hrs

Table 1: Procedures involved, location and estimated duration of visits 1 and 2.

After the baseline assessment is complete, subjects will be randomly allocated to one of two groups using a random allocation software. Participants will be asked to

attend **3 treatments sessions/week for 6 consecutive weeks**. These sessions will be conducted at the CTSI’s Clinical Research Center at Goodman Hall and will last approximately 110 min. A research coordinator will supervise the patients during the sessions. On each session, subjects will initially have their body weight and blood pressure measured and recorded. Next, patients will be asked to change into the water-circulating pants (Figure 3) and lay in semi-recumbent position. The garments will be connected to the water pump and the treatment will be applied for 90 min. In the high-heat group, hot water will be circulated through the garment with the goal of increasing skin temperature to 40°C, while thermoneutral water (33°C) will be used in the low-heat group. Subjects will be allowed to drink water ad libitum during the sessions but will not be allowed to consume food. At the end of the session, body weight and blood pressure will once again be recorded. The research coordinator will measure temperature (sublingual measurements) and blood pressure every 15 minutes during the treatment and will also inspect the skin in the legs to look for potential signs of injury or adverse reactions to the treatment. The subject will be asked to complete a heat sensation scale every 15 minutes during the treatment. The research coordinator will clean the garment after each use using a hospital-grade disinfectant spray. The garment will also be washed in a washing machine every week.

Figure 3: Water-circulating garment system for thermotherapy application

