Outcome measurements will be repeated after 9 sessions (3 weeks) and at the end of the treatment period (18 sessions). The protocol for these visits will be similar to visit 2, with the addition of quality of life assessment. The procedures involved are detailed on table 2. This visit is expected to last approximately 4.5 hrs. Subjects will be asked to fast overnight prior to attending this session but will be permitted to take their usual morning medication regimen.

Visit #	Procedures	Location	Duration
3 and 4	1) Leg MRI (reactive hyperemia) 2) Catheter placement and venous blood draw 3) Measurement of ankle-brachial index 4) Quality of life assessment 5) Assessment of cutaneous vascular function 6) 6-min walking test	Imaging Research Facilities and CTSI’s Clinical Research Center at Goodman Hall	4.5 hrs

Table 2: Procedures involved, location and estimated duration of visits 3 and 4.

Outcome Measures:

Reactive Hyperemia in the Popliteal Artery: Blood flow in the popliteal artery of the most symptomatic leg will be measured using MRI. We employed this technique in our initial study (IRB Protocol #1409063619). After the knee coil and the occlusion cuff are positioned on the most symptomatic leg, participants will be allowed to rest quietly for 15 min. Resting leg blood flow measurements and brachial systolic blood pressures will be completed every 5 min during this period. Next, a blood pressure cuff firmly wrapped around the lower thigh will be inflated to 75 mmHg above systolic blood pressure, or 250 mmHg, whichever is lower, for 5 min (8). Hyperemic flow will be measured for 10 min after cuff deflation. Flow reserve will be defined as the absolute difference between maximum hyperemic flow after cuff release and resting flow (9).

Cutaneous Microvascular Function: Laser-Doppler flowmetry probes, seated in the center of local skin heaters (Moor Instruments, UK), will be used to measure red blood cell flux, an index of skin blood flow (SkBF). Baseline SkBF will be recorded for 10 min after which local skin temperature will be increased to 39°C (0.1°C/s) and maintained at this level until a plateau is achieved (~40 min). Next, the local skin temperature will be elevated to 43°C, to induce maximal vasodilation. Cutaneous vascular conductance (CVC) will be calculated as laser-Doppler flux divided by mean arterial pressure (MAP), measured throughout the study via brachial artery oscillation, and normalized to maximal vasodilation (%CVC_{max}) (10, 11).

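### The fasting rule for Visits 2, 3 and 4 permits usual morning medicines with no exception for glucose-lowering drugs, although controlled diabetes is eligible

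*Protocol*

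**What the plan says.** Protocol section 5.0 gives one instruction on food and medicines for the mornings of the outcome visits. It appears in the Visit 2 text and again, in the same words, for Visits 3 and 4: "Subjects will be asked to fast overnight prior to attending this session but will be permitted to take their usual morning medication regimen".

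Section 3.0 lists one diabetes exclusion: "Uncontrolled Diabetes (HbA1C > 8.5 measured within 3 months prior to date of consent"). No criterion limits insulin or other glucose-lowering drugs. The MRI list in the same section includes "Insulin or infusion pump", but only as a reason to omit the scan, because "patients that have contraindications to MRI will be included in the study but will not be allowed to participate in the MRI procedure".

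Visit 2 is planned at about 4 hours and Visits 3 and 4 at about 4.5 hours each. In Tables 1 and 2 the walk test is the last procedure.

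The protocol sets a food rule elsewhere. During the heat-treatment sessions patients "will not be allowed to consume food". Visits 2 to 4 have no matching sentence, either way.

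Medicines are recorded at Visit 1: "Subjects will then be asked about comorbid conditions, claudication history, and current medications". The text on potential risks covers the walk, leg heating, blood sampling, blood pressure and oxygenation measurement, MRI and cuff occlusion. It names neither fasting nor low blood glucose.

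**The concern.** Fasting and glucose-lowering treatment interact. A dose meant to be followed by breakfast can lower blood glucose too far if breakfast is missed. The only written instruction about medicines on these mornings permits the usual regimen, and it makes no distinction for the drugs where the fast matters. The patient may take the dose at home, before any staff contact.

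What is at stake is participant safety at the three visits that supply the trial outcomes. The point does not concern the sample size, the comparison between arms or the analysis models.

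**Working it through.** The plan gives no figure on this point, so there is none to reproduce. The check sets the provisions side by side and then adds up the stated times.

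**1. Who the rule reaches.** The exclusion applies when HbA1c is above 8.5. Diabetes with HbA1c of 8.5 or below therefore remains eligible, on any treatment. Other exclusions, such as peripheral neuropathy, may reduce the number of patients with diabetes but do not remove them.

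**2. What the rule allows.** The overnight fast applies to every patient at Visits 2, 3 and 4, and the permission covers all usual morning medicines. For a patient on insulin or a similar drug, the two parts together allow a normal dose without food.

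**3. Whether this depends on when the fast ends.** It does not. If the fast ends on arrival, a dose taken at home has still been taken before food. If it runs on through the fasted measures, the interval is longer. The gap is in the medication clause under either reading.

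**4. Stated times at Visit 2** (minutes, section 5.0):
- MRI: 15 rest + 5 occlusion + 10 hyperaemic flow = 30
- Supine rest before the pressure measurements: 10
- Skin heating test: about 60
- Before the walk: 30 + 10 + 60 = about 100, or 10 + 60 = about 70 for a patient who does not have the MRI

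The blood draw comes before the skin test ("a blood sample (20 ml) will be taken and the catheter will be removed"), so about 60 of these minutes follow it.

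**5. Stated times at Visits 3 and 4.** The visit is longer by 4.5 − 4.0 = 0.5 hours = 30 minutes. Table 2 places the questionnaires after the blood draw: "4) Quality of life assessment 5) Assessment of cutaneous vascular function 6) 6-min walking test". Assuming that 0 to 30 of the extra minutes fall there, about 60 to 90 minutes lie between blood draw and walk.

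The times in steps 4 and 5 leave out transfers, set-up and the ankle-brachial measurements. They describe the schedule and do not show how long anyone is fasted.

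**6. Number of visits.** Affected visits = 3 × k, where k is the number of patients on glucose-lowering drugs. The documents do not give k. Purely as assumptions, out of 2 × 16 = 32 planned patients:

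| k (assumed) | Share of 32 | Visits (3 × k) |
|---|---|---|
| 3 | 9% | 9 |
| 8 | 25% | 24 |
| 13 | 41% | 39 |

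These are counts of visits under the rule. They do not measure risk.

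**The case against.** Four arguments can be made on the other side.

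- **The rule permits and does not direct.** Staff or the patient's own clinician remain free to advise a reduced or omitted dose, and they have the history, examination and medication list from Visit 1. This is true, but nothing in the protocol prompts that advice, and a patient who takes the usual dose has complied.

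- **There are other safeguards.** The investigator may exclude unsuitable patients, a nurse places the catheter, heart rate and blood pressure are monitored during the skin test, and patients stop walking if they stagger, sweat or feel dizzy. These count for something. None is an instruction about glucose, and the stop rule acts only after symptoms and only during the walk.

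- **Patients may have been told separately.** Section 4.0 promises detailed instructions and a consent form, and the consent pages are not available for review. Suitable advice there cannot be ruled out. What is shown is a gap in the protocol text; whether patients went uninstructed is not known.

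- **Food is not forbidden at these visits.** This stands. A reader might infer that the walk is done fasted at the end of a long visit. The documents do not support that. The fast is asked for before attendance, no sentence bars food at Visits 2 to 4, and where the authors wanted to bar food, at the treatment sessions, they said so. Equally, no food is offered.

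A reader might also take the insulin-pump entry to mean that insulin users were expected in the trial. It is one line in a generic list of MRI devices. It is consistent with their inclusion and shows no more than that.

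**Conclusion.** The point holds as a minor safety fix. The medication clause for Visits 2, 3 and 4 lacks an exception for glucose-lowering drugs, eligible patients may be taking them, and the risk text does not mention low blood glucose. Each affected patient meets the rule three times.

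The wording of the rule is certain. The clinical consequence is less so: it assumes that at least one enrolled patient takes such a drug in the morning and receives no separate advice. The number affected is unknown and no event rate can be given.

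A reader might go further and infer a bias between arms or a threat to the walk result. The same rule applies to both groups, and nothing in the documents points to a difference. Nor can the total of scheduled visit time be read as hours of fasting or as a measure of hazard.

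**What to change.** In both places in section 5.0, add to the permission for morning medicines: except glucose-lowering medicines, which are held or adjusted on clinician advice until the patient eats. In addition:

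- use the Visit 1 medication record to identify these patients before Visit 2;
- keep each patient's approach the same at Visits 2, 3 and 4;
- add low blood glucose to the potential risks.

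This costs one clause in two places, a short operational instruction and one risk entry, with no extra visits or patients.

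The downside is that, in this subgroup, drug state during the fasted measures may differ from usual. A constant approach limits the effect on within-patient change, since the SAP takes Visit 2 as baseline for the MRI, blood and skin measures. For the walk, the SAP takes the better of Visits 1 and 2 as baseline, and no fast is stated for Visit 1; the fix leaves that as it is.

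A meal before the walk for these patients is optional and not part of the required change. It would alter conditions for one subgroup on the outcome used to size the trial, and the text does not forbid food as it stands.

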Leg heating: Hot water (47-50°C) will be perfused through the water-circulating garment with goal to increase skin temperature in the calf to 40°C. It is possible that the tubes in contact with the skin could cause discomfort due to a sensation of warmth/heat. Should the tubing that is in contact with the skin cause discomfort we will readjust the suit or turn down the temperature of the water. Ninety minutes of heating will likely lead to skin redness and flushing, which are typical responses to local heating. These effects are temporary and will fade once the heating stimulus is terminated. Once instance of skin being burned to the point of blistering has occurred. The research coordinator will examine the patient's skin during each treatment session for potential signs of injury or adverse reactions to the treatment.

A sophisticated, research-grade heated bath circulator will be used to circulate water through the garment. The actual device we use (SC100) and its technical specifications are displayed in the document entitled "SAHARA S21 Stainless-Steel Heated Bath Circulators." The temperature stability of this heated bath circulator is 0.02°C. This is a remarkably small variation, which supports the notion that there are no risks of sudden oscillations water temperature.

The actual temporal behavior of skin temperature during 90-minutes of thermotherapy application is shown on the figure on page 4 of the protocol. There are no abrupt changes in temperature. The response follows an exponential rise to a peak of around 39.5°C at 90 minutes. This temperature is safe and far below the temperature required to burn the skin, which is typically above 43°C.

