Our initial study revealed that the proposed protocol leads to a progressive increase in leg skin temperature from a baseline of 33°C to ~39.5°C. A research coordinator will supervise each treatment session. If the patient experiences any discomfort or burning sensations, the coordinator will readjust the suit or turn down the temperature of the water. Subjects will be reminded to remain in a semi-recumbent position during treatment and will also be asked to rate heat sensation every 15 minutes using a thermal sensation scale to monitor for excessive heat levels on the skin. If subject reports a grade of 3 ("Hot") or above, or any discomfort, the coordinator will readjust the suit and turn down the temperature of the water. If, after reducing the temperature and readjusting the suit the patient again reports a grade of 3, we will keep repeating the aforementioned steps until the score drops down and the patient feels comfortable. Water temperature

will be assessed and recorded every 15 minutes using the temperature display on the pump.

In preliminary experiments we observed that thermotherapy application induces a minor reduction in blood pressure in some patients. The research coordinator will measure blood pressure prior to and every 15 minutes throughout the application. If the patients experience dizziness, lightheadedness or any other symptom of hypotension, the therapy will be terminated and the participant will be placed supine with the legs elevated. Blood pressure will be checked every 5 minutes until the symptoms disappear and blood pressure returns to baseline levels.

Venous blood sampling: During catheter insertion there is a risk of pain from the needle. Bleeding, local swelling, bruising and formation of a hematoma might also occur around puncture site. By using appropriate phlebotomy techniques, the risks associated with catheter placement and repeated sampling are minimized.

Blood pressure measurements: There are no risks associated with the blood pressure measurements.

Measurement of calf muscle oxygenation: There are no risks associated with blood pressure measurements.

MRI scan: Potential risks associated with MR imaging include:

- Claustrophobia: the confining conditions of the MR scanner can cause claustrophobia. If the patient experiences claustrophobia the scan will be stopped.

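### Leg skin is inspected at every session, but not required on bare legs before the garment goes on, and no written rule holds heating when a burn, blister or open wound is seen

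*Protocol*

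**What the plan says.** Section 5.0 of the protocol gives the order of each session. At the start, "subjects will initially have their body weight and blood pressure measured and recorded. Next, patients will be asked to change into the water-circulating pants". During the 90 minutes of heating, the coordinator is to "measure temperature (sublingual measurements) and blood pressure every 15 minutes during the treatment and will also inspect the skin in the legs". After heating, "At the end of the session, body weight and blood pressure will once again be recorded". The leg-heating part of the risk text in the same section repeats the inspection duty: the coordinator examines the patient's "skin during each treatment session for potential signs of injury or adverse reactions to the treatment".

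That risk text describes the hazard in three ways:
- It reports a past injury: "Once instance of skin being burned to the point of blistering has occurred".
- It expects redness and flushing from the heating and says of them: "These effects are temporary and will fade once the heating stimulus is terminated".
- It gives the usual course of skin temperature: "The response follows an exponential rise to a peak of around 39.5°C at 90 minutes". It sets this against a typical burn level above 43°C, while the water in the tubes is at 47-50°C.

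The stopping rule is: "If the patients experience dizziness, lightheadedness or any other symptom of hypotension, the therapy will be terminated". For discomfort, a burning sensation or a rating of hot, the coordinator adjusts the suit or cools the water, and for repeated hot ratings does so again until the patient is comfortable.

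Elsewhere, section 3.0 excludes patients with an open wound or ulcer on the limb and those with neuropathy or numbness in the legs. Section 6.0 tells an injured patient to contact the investigators. Section 7.0 covers only withdrawal by the patient's own choice. The SAP does not address skin findings.

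**The concern.** Two things are missing. First, no step requires someone to see the bare legs between arrival and putting on the garment; weight and blood pressure are the only checks listed there. Second, the inspection that is required leads to no stated action. The written responses depend on what the patient feels, not on what the coordinator sees.

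What is at stake is repeat injury. Some burns show only after the patient has gone home, and a patient may acquire a wound between visits for unrelated reasons. A session run exactly as written could then heat a leg that would now fail the entry criterion on open wounds. The trial's estimates are not at issue; this is participant safety in the treatment procedure.

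**Working it through.** No figure in the plan is in dispute. The check is whether any section supplies either missing element, followed by simple arithmetic on exposure and cost.

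**1. Where a bare-leg look could be required (protocol section 5.0)**

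| Point in the session | Checks listed | Bare-leg look required? |
|---|---|---|
| Before the garment | Weight, blood pressure | No |
| During heating | Temperature, blood pressure, heat rating, water temperature; skin inspection in the same sentence as the first two | Inspection required; exposure of the skin not described |
| After heating | Weight, blood pressure | No |
| Risk text, any time in the session | Skin examination | Permitted before dressing, not required |

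**2. What each trigger leads to (protocol sections 5.0 to 7.0)**

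| Trigger | Stated response | Heating stopped or held? |
|---|---|---|
| Symptoms of hypotension | Therapy ended, patient laid supine | Yes |
| Discomfort or burning sensation | Suit adjusted or water cooled | No |
| Hot rating, repeated | Adjust and cool until comfortable | No |
| Burn, blister or wound seen by the coordinator | None stated | No |
| Injury from taking part (section 6.0) | Patient contacts investigators | No |
| Patient's own wish (section 7.0) | Voluntary withdrawal | Only if the patient chooses |

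**3. Sessions exposed.** Three sessions a week for 6 weeks is 3 × 6 = 18. Session 1 follows a baseline physical examination (Table 1) and the open-wound exclusion, so the gap concerns sessions 2 to 18: 18 − 1 = 17 sessions per participant.

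**4. Temperature margin.** The stated skin peak is 43 − 39.5 = 3.5°C below the stated burn level, so burns should be uncommon. The circulating water is 47 − 43 = 4°C to 50 − 43 = 7°C above that level, and the risk text notes that the tubes touch the skin. The 3.5°C margin describes the reported skin-temperature course, not necessarily every contact point. The per-session checks include oral temperature and water temperature at the pump but list no skin temperature, so apart from the patient's own sensation the visual inspection is the only listed check on the skin.

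**5. What the earlier look adds.** The protocol expects flushing during heating that fades afterwards. A look before the next session comes after that fading, on average 7 / 3 = 2.3 days later. This is an average only, since no minimum spacing is set. It helps mainly with a burn that could pass for flushing during heating, or one that appeared after the previous session.

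**6. Cost.** Non-heating time is about 110 − 90 = 20 minutes per session. Assume 1-2 minutes before dressing and 0.5-1 minute on removal:
- per session: 1 + 0.5 = 1.5 to 2 + 1 = 3 minutes, or 1.5/20 = 7.5% to 3/20 = 15% of the non-heating time;
- per participant: 18 × 1.5 = 27 to 18 × 3 = 54 minutes over the course.

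**The case against.** The strongest reply is that an inspection is already required at all 18 sessions, and that a session, as the protocol uses the word, includes changing clothes. A coordinator who looks at the legs while the patient changes complies with the text. Supervision, heat ratings and water-temperature records every 15 minutes, cooling for any discomfort, and the exclusion of patients with numb legs all lower the risk. A sensible coordinator would also stop on seeing a blister. This stands as a limit on the size of the problem. It does not supply the missing rule: the protocol writes a stop for dizziness and none for a visible burn.

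A reader might also infer several stronger things that the documents do not support:
- *The inspection is fixed during heating.* The 15-minute schedule clearly governs temperature and blood pressure; its reach over the skin inspection is loose, and the risk text leaves the timing open.
- *The inspection cannot work because the legs are covered.* The garment fits tightly, but the protocol does not say how the skin is exposed for inspection, and its figure is not available here.
- *Flushing would hide any injury.* It might mask early redness from a burn; it would not hide a blister or an open wound.
- *The recorded burn was missed, or the leg was heated again.* The text gives no date, setting, arm or means of detection.
- *The less affected leg is never seen between baseline and the end.* Visit 3, after 9 sessions, repeats ankle pressures as well as taping probes to one leg. It is still one outcome visit, not an injury check.

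**Conclusion.** The point holds as a gap in the written procedure: no bare-leg inspection is required before the garment goes on, and no action is attached to a visible skin injury. The missing hold is the weightier half; the pre-garment look mostly settles the timing of an inspection that already exists.

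The gap applies to 17 of the 18 sessions per participant. How often it would matter cannot be estimated: the documents give one burn, without a denominator or circumstances. The conclusion rests on the text as written, not on any assumption that staff would act carelessly. It should be fixed because a burn has been recorded, the water is hotter than the stated burn level, and the remedy is short. It affects no endpoint definition, sample size or planned analysis.

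**What to change.** In section 5.0, in the description of treatment sessions, add: *At every session, in both arms, the coordinator inspects the bare skin of both legs before the garment goes on, and briefly again on removal, and records the findings.*

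There, and beside the hypotension rule in the leg-heating risk text, add: *If a burn, blister or open wound is seen at any check, heating is stopped or not started until an investigator clears it.*

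Include both arms so that procedures match under the sham design. The low-heat water is at 33°C, so the burn reason does not reach that arm, but a new open wound can occur in either.

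The cost is the assumed 1.5 to 3 minutes per session, with the coordinator already present, and occasional postponed or missed sessions. These would fall mostly in the high-heat arm. They should be recorded by arm, and the protocol should say whether a held session is made up, because treatment is set at 6 consecutive weeks and visit 3 is tied to 9 sessions.
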